9.2 Adverse Events

Adverse events (AEs) will be summarized and presented using primary MedDRA System Organ Classes (SOCs) and preferred terms (PTs) according to the version of the MedDRA coding dictionary used for the study at the time of database lock. The actual version of the MedDRA coding dictionary used will be noted in the AE tables and in the clinical study report.

9.2.1 Treatment-Emergent Adverse Events

An AE will be considered a treatment emergent adverse events (TEAE) if the AE began or worsened (increased in severity or became serious) on or after the date of the first study intervention. However, an AE that occurs more than 30 days after the last dose of study intervention will not be counted as a TEAE. Per the AE/SAE training manual, a new AE record will be created with a new AE onset date for any AE that worsens. Therefore, TEAEs can simply be identified as those AEs with recorded onset date on or after the date of the first study intervention and within 30 days after the last dose of study intervention.

An AE will be considered a treatment emergent serious adverse event (TESAE) if it is a TEAE that additionally meets any serious adverse event (SAE) criterion.

9.2.2 Adverse Event Overview

Adverse events will be classified into ocular AEs and nonocular AEs. An ocular AE will be determined as indicated on the AE form of eCRF (marked “OD” or “OS” to the question of “what was the location of the adverse event?”), and thus are not limited to AEs with primary SOC of eyes.

An overview of AEs will be presented consisting of the number and percentage of participants experiencing at least one event for each of the following AE categories:

- Any treatment-emergent AE (ocular and non-ocular)
- Any treatment-emergent AE with reasonable possibility of being related to study drug according to the investigator (ocular and non-ocular)
- Any serious treatment-emergent AE
- Any treatment-emergent AE leading to discontinuation of study drug
- Any treatment-emergent AE leading to death
- Any treatment-emergent AE: headache of special interest
- Any treatment-emergent AE: visual disturbance of special interest
- All deaths

Overall summary of TEAEs will be provided by study intervention group on a per-participant level.

9.2.3 Treatment-Emergent Adverse Events by SOC and/or PT

Treatment-emergent adverse events will be summarized by SOC and PT; by maximum relationship to study drug as assessed by the investigator (e.g., reasonable possibility or no reasonable possibility) and SOC and PT; by maximum severity and SOC and PT. Specific adverse events will be counted once for each participant for calculating percentages, unless stated otherwise. In addition, if the same adverse event occurs multiple times within a participant, the highest severity and level of relationship to investigational product will be reported.

Nonocular TEAEs will also be summarized by SOC and PT.

Ocular TEAEs will be summarized by preferred term and maximum relationship to study drug assessed by investigator.

9.2.4 SAEs (Including Deaths) and Adverse Events Leading to Study Drug Discontinuation

All the SAEs (including deaths) and AEs leading to study drug discontinuation will be summarized by SOC and PT and presented in listing format. The listing will indicate if an AE is ocular or nonocular. All nonocular SAEs (including deaths) and nonocular AEs leading to study drug discontinuation will be summarized by SOC and PT.

9.2.5 Adverse Events of Special Interest

Headache of special interest and visual disturbance of special interest are the adverse events of special interest. List of PT for AEs of special interest is provided in [Appendix B](#). The TEAEs of special interest will be summarized by study intervention group.

A similar summary will be provided for visual disturbance TEAEs of special interest. The definition of these adverse events of special interest is described in [Appendix B](#). The list of preferred terms used for the analysis will be reviewed and finalized prior to database lock.

9.3 Vital Signs

Vital signs are collected only at screening and data will not be analyzed.

9.4 Pregnancy

Positive test results for women of childbearing potential will be listed.

9.5 Ocular Safety Analyses

9.5.1 Slit-lamp Biomicroscopy and Ophthalmoscopy

All biomicroscopy and ophthalmoscopy examinations findings will be coded using the MedDRA dictionary.

The number and percentage of participants with biomicroscopy or ophthalmoscopy findings of greater than 1-grade severity increase from baseline for findings with a severity grade, or a positive status change from absence at baseline to presence at postbaseline (not associated with a severity grade), will be summarized by preferred term and study intervention group.

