**Table 1-1 Schedule of Visits and Procedures**

Procedures	Study Days (Visits)							Notes	
	Screening (Visit 1)	Randomization/ First Dosing Visit (Visit 2)	First Driving Visit (Visit 3)		Washout Period	Second Dosing Visit (Visit 4)	Second Driving Visit/ Early Exit (Visit 5)		
	Days -30 to -1	Day 1 (to be scheduled between 08:00 and 10:00)	Days 8 to 15		7 to 42 days	Days 15 to 57 (to be scheduled between 08:00 and 10:00)	Days 22 to 71		7- to 14-day study intervention adaptation period between Visits 2/3 and 4/5
Visit Windows			Before Dosing	After Dosing			Before Dosing	After Dosing	Before dosing (before study intervention instillation) and after dosing (approximately 1 hour after study intervention instillation)
Informed consent	X								
Iris color assessment	X								
Demography	X								
Medical and ophthalmic history	X								
Confirm participant did not dose at home			X				X		On the day of both driving visits, confirm that the participant did not instill study intervention at home.
Practice driving test			X				X		Participant will complete at least 1 practice session on the driving course at Visits 3 and 5.
Prestudy/ concomitant medication query	X	X	X	X		X	X	X	
AE query	X	X	X	X		X	X	X	Please see Section 8.3 and Section 10.2.

Procedures	Study Days (Visits)							Notes	
	Screening (Visit 1)	Randomization/ First Dosing Visit (Visit 2)	First Driving Visit (Visit 3)		Washout Period	Second Dosing Visit (Visit 4)	Second Driving Visit/ Early Exit (Visit 5)		
Visit Windows	Days -30 to -1	Day 1 (to be scheduled between 08:00 and 10:00)	Days 8 to 15		7 to 42 days	Days 15 to 57 (to be scheduled between 08:00 and 10:00)	Days 22 to 71		7- to 14-day study intervention adaptation period between Visits 2/3 and 4/5
			Before Dosing	After Dosing			Before Dosing	After Dosing	Before dosing (before study intervention instillation) and after dosing (approximately 1 hour after study intervention instillation)
Vital signs	X								Blood pressure and heart rate measured after participant has been at rest (seated) for at least 5 minutes. Please see Section 8.2.2.
Urine pregnancy test	X	X	X			X	X		WOCBP only. Please see Section 8.2.3.
OSDI	X								Please see Section 0, Item 4.02 (exclusion criteria).
NEI VFQ 25	X								Please see Section 5.1, Item 2.02 (inclusion criteria).
Slit-lamp biomicroscopy	X	X	X	X		X	X	X	Please see Section 8.2.1.1.

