**Conjunctiva (Bulbar):**

Hyperemia

0	(None)	=	No hyperemia
+0.5	(Trace)	=	Minimal (trace) flush, reddish color
+1	(Mild)	=	Mild flush, reddish color
+2	(Moderate)	=	Bright red color
+3	(Severe)	=	Deep, bright, diffuse redness

Edema

0	(None)	=	No edema
+0.5	(Trace)	=	Localized, minimal (trace) swelling
+1	(Mild)	=	Localized, mild swelling
+2	(Moderate)	=	Diffuse, moderate swelling
+3	(Severe)	=	Diffuse, severe swelling

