**Lens:**

Lens Assessment:

Use biomicroscopic examination, indirect lenses, direct/indirect ophthalmoscopy, etc, as appropriate, to visualize.

Lens Status:

The lens will be evaluated for pathology. If pathology is present, it will be described.

Cataract Assessment:

Under dilated examination, the presence and severity of nuclear, cortical, and posterior subcapsular cataract lens opacities will be evaluated. At the first dilated examination, each type of cataract, if present, will be graded using the scale below. At the last follow-up dilated examination, each type of cataract will be assessed for change from baseline and if changed, the current severity will be graded using the scale below:

0	=	None
+1	=	Mild
+2	=	Moderate
+3	=	Severe

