7.4 Data Collected but Not Analyzed

Iris color assessment, vital signs, ocular surface disease index, National Eye Institute Visual Function questionnaire 25, fluorescein corneal stain, gonioscopy/angle assessment, binocular mesopic and photopic high contrast, BCDVA and DCNVA assessments, manifest refraction and dilated fundoscopic examination results are collected only at Screening and will not be analyzed. Any clinically significant vital sign findings or abnormal pupil dilation findings will be captured as an adverse event and summarized accordingly.

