9.0 Safety Analyses

9.1 General Considerations

- The safety endpoints will be analyzed with descriptive statistics using the safety population.
- The safety results will be presented by study intervention group.
- The results for “AGN-190584” group will be based on Period 1 data for study intervention sequence “AGN-190584 followed by vehicle”, and Period 2 data for study intervention sequence “vehicle followed by AGN-190584”.
- The results for “vehicle” group will be based on Period 2 data for study intervention sequence “AGN-190584 followed by vehicle”, and Period 1 data for study intervention sequence “vehicle followed by AGN-190584”.
- For each study period, the baseline for safety parameters will be the last assessment prior to the first administration of study intervention in the period unless specified otherwise.
- For each study period, the change from baseline values will be computed as the postbaseline value minus the baseline value (defined above) for that study period.
- Continuous variables will be summarized by number of participants with observed values (n), mean, standard deviation, median, 1st and 3rd quartiles, minimum, and maximum.
- Categorical variables will be summarized by number of participants with observed values (n), frequency counts (n1) and percent of participants with observed values.

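### SAP 9.5.1 counts graded slit-lamp findings only above a 1-grade increase, so mild-to-moderate and moderate-to-severe worsening stay out of the summary; its ophthalmoscopy part conflicts with the examination schedule

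*SAP*

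**What the plan says.** Slit-lamp biomicroscopy is a named safety endpoint (SAP 3.3). Under the schedule (protocol Table 1-1) it is done at all five visits, before and after dosing at both driving visits. Protocol 9.4.2.2 leaves the method for such variables to the SAP.

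SAP 9.5.1 gives two routes into the summary table. Graded findings enter as "findings of greater than 1-grade severity increase from baseline for findings with a severity grade". Findings without a grade enter on first appearance, whatever their extent. Both routes cover biomicroscopy and ophthalmoscopy. SAP 9.1 sets the reference point separately for each period: "the baseline for safety parameters will be the last assessment prior to the first administration of study intervention in the period".

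Protocol 8.2.1.1 supplies the grades. For bulbar hyperemia, for example, the scale goes from 0 through trace at +0.5 ("Minimal (trace) flush, reddish color"), mild at +1 and moderate at +2 to severe at +3 ("Deep, bright, diffuse redness"). Lid edema and erythema, conjunctival hyperemia and edema, corneal edema and superficial punctate keratopathy use the same five values.

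On ophthalmoscopy, Table 1-1 has dilated fundoscopy at screening only, and SAP 7.4 says that "dilated fundoscopic examination results are collected only at Screening and will not be analyzed". Protocol 8.2.1.3 says "At the last follow-up dilated examination, each type of cataract will be assessed for change from baseline".

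**The concern.** A threshold strictly above 1 grade, on a scale whose upper steps are exactly 1 apart, removes single-step worsening in the part of the scale that matters most clinically: mild to moderate and moderate to severe. The SAP also does not say whether a grade is a unit of the numeric scale or one category. That choice alone decides whether a new mild finding, such as mild hyperemia or mild keratopathy after dosing, is counted.

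The first-appearance route cannot recover these changes, because it is reserved for findings that carry no grade. At stake is how completely a named safety endpoint is described in the comparison with vehicle.

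The ophthalmoscopy part is a separate matter. Section 9.5.1 plans a change from baseline for an examination that the schedule never repeats.

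**Working it through.** There is no stated figure to reproduce. The check applies the counting rule to the scale and then sets the examination passages side by side.

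**Inputs.** Scale values 0, 0.5, 1, 2, 3 (protocol 8.2.1.1). Rule: increase greater than 1 grade (SAP 9.5.1). Five values give 5 × 4 / 2 = 10 possible upward moves.

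**Method.** For each move, take the difference in scale units (end value minus baseline value) and the number of ordinal steps (categories moved). Then apply three tests: more than 1 unit, more than 1 step, and, for comparison, at least 1 unit.

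| Move | Units | Steps | > 1 unit | > 1 step | ≥ 1 unit |
|---|---|---|---|---|---|
| none to trace | 0.5 | 1 | no | no | no |
| none to mild | 1 | 2 | no | yes | yes |
| none to moderate | 2 | 3 | yes | yes | yes |
| none to severe | 3 | 4 | yes | yes | yes |
| trace to mild | 0.5 | 1 | no | no | no |
| trace to moderate | 1.5 | 2 | yes | yes | yes |
| trace to severe | 2.5 | 3 | yes | yes | yes |
| mild to moderate | 1 | 1 | no | no | yes |
| mild to severe | 2 | 2 | yes | yes | yes |
| moderate to severe | 1 | 1 | no | no | yes |
| **Counted** | | | **5 of 10** | **6 of 10** | **8 of 10** |

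**Result.**
- Mild to moderate and moderate to severe fail the SAP test on both readings.
- The only upward move from a moderate baseline is to severe, so no worsening from that baseline can be counted.
- The two readings differ in one move only, none to mild.
- All three moves to severe from a lower baseline than moderate are counted.

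**Other places where the changes could appear.** SAP 9.1 gives generic formats for continuous and categorical variables but specifies no slit-lamp table. SAP 9.5.1 is the only slit-lamp specification and plans neither a shift table nor a listing. SAP 7.4 states a route to adverse events for vital signs and abnormal pupil dilation; there is no such statement for slit-lamp grades.

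**Ophthalmoscopy.** Table 1-1 gives one dilated examination, at Visit 1, and none at Visits 2 to 5, so the number of scheduled post-baseline examinations is 0. SAP 7.4 agrees with that schedule. SAP 9.5.1 and the cataract paragraph of protocol 8.2.1.3 both presuppose a later examination.

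**The case against.** The strongest reply is that the threshold is the analyst's choice. The protocol sets none, the table is descriptive with no test attached, and the rule is the same for both treatments. That stands: the threshold contradicts nothing in the protocol. The point is that the summary loses information already collected.

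A second reply is that the excluded moves will be rare. Exclusions 4.01, 4.03, 4.06 and 4.09 remove most eyes with relevant disease, and baseline is reset after a washout of at least 7 days. This is plausible for moderate baselines. It is not assured: no entry criterion caps the slit-lamp grade, and exclusion 4.02 removes dry eye only when both the staining and the OSDI limits are met. The documents give no baseline distribution.

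A third reply is that a worsening has another outlet. An adverse event includes any unfavorable sign (protocol 10.2.1), events are queried at every visit, ocular events are tabulated by preferred term (SAP 9.2.3), and all events are listed (protocol 9.4.2.1). This also stands, but it depends on the investigator recording the change as an event.

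A reader might go further in four ways that the documents do not support:
- *That new severe findings are missed.* They are counted from none, trace or mild; only moderate to severe is lost.
- *That a finding shows only once it is moderate, so the table is clean by construction.* This needs both the scale-unit reading and baselines that are mostly 0. On the ordinal reading a new mild finding is counted.
- *That counting trace to moderate but not moderate to severe is inconsistent.* The first is the larger change on either measure (1.5 against 1 unit, 2 steps against 1), so a change-from-baseline rule treats them coherently.
- *That the ophthalmoscopy rows would be taken as evidence of a post-treatment fundus check.* With no post-baseline data there is nothing to count, and how a reader would take an empty row is conjecture.

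**Conclusion.** The concern holds for the SAP 9.5.1 summary. It omits mild-to-moderate and moderate-to-severe worsening on either reading of grade, and new mild findings as well if grade means scale units. Five or 6 of the 10 possible upward moves are counted, depending on a definition that the SAP does not give. These are counts of types of move, not of expected events; the documents give no incidence from which to estimate how many participants would be affected.

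The conclusion assumes that the grades analyzed are the protocol's five values and that no unstated shift table or listing is planned. The effect is limited to descriptive safety reporting. The primary analysis, sample size and type I error are untouched. A change is worthwhile because the endpoint is named and the remedy is cheap.

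The ophthalmoscopy conflict is real but largely editorial, since no post-baseline examination is scheduled.

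**What to change.** In SAP 9.5.1, before database lock:
1. State that grade means the protocol's numeric value.
2. Add a row for increases of at least 1 grade. This counts 8 of 10 moves; only the two half-grade moves, none to trace and trace to mild, stay out.
3. Keep the row for increases above 1 grade.
4. List every finding that worsens to +3, from any baseline.

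If at least 1 grade was what the authors meant all along, this is mainly a wording correction.

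The cost is SAP text, one extra row per preferred term and a short listing, all from data already collected. The downside is a longer table with more mild findings under both treatments.

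Separately, reconcile four places: the ophthalmoscopy wording in SAP 9.5.1, SAP 7.4, the cataract paragraph of protocol 8.2.1.3, and the dilated fundoscopy row of Table 1-1. Which examination schedule is intended is for the sponsor to settle. If the answer changes protocol text, it costs a protocol correction as well as a SAP edit.

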9.5.2 Mesopic and Photopic Binocular HDVA

Binocular HDVA will be tested using logMAR charts at 4 m under 2 lighting conditions: mesopic luminance (10 to 11 lux) and photopic luminance (≥ 251 lux) under normal room lighting. Testing will be conducted with the optimal distance refractive correction. Forced choice letter-by-letter scoring will be used for each test and the total number of correct letters or the highest value (number) of the grid identified (as applicable) will be collected for each eye.

The total number of correct letters or the highest value (number) of the grid identified (as applicable) will be summarized by study intervention group, at the participant level for the screening test, before dosing at each driving test visit, and after dosing at each driving test visit for each lighting condition. The change at each driving test (post dosing assessment

minus pre dosing assessment) will also be summarized by study intervention group, at the participant level.

9.5.3 Intraocular Pressure

Intraocular pressure (IOP) will be measured for each eye, IOP change from baseline will be calculated for each eye and the summary will be based on the eye with greater decrease from baseline.

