**Figure 1-1 Study Schema**

### 1.3. Schedule of Activities (SoA)

Study procedures are recommended to be completed in sequence as listed in the schedule below (Table 1-1).

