			Before Dosing	After Dosing			Before Dosing	After Dosing	Before dosing (before study intervention instillation) and after dosing (approximately 1 hour after study intervention instillation)
Photopic manifest refraction (distance and near)	X								Please see Section 8.2.1.2.
Mesopic conditions: allow for dark adaptation (5 to 10 minutes in mesopic conditions). Perform under mesopic conditions (3.2 to 3.5 cd/m  ; 10 to 11 lux at target).			X	X			X	X	Carry out in the order specified.
Mesopic, high-contrast, binocular HDVA			X	X			X	X	At the driving visits, measurement is conducted with habitual correction for OU only.
Mesopic pupil diameter			X	X			X	X	Please see Section 8.1.7.
Halometer			X				X		Please see Section 8.1.8.

Procedures	Study Days (Visits)							Notes	
	Screening (Visit 1)	Randomization/ First Dosing Visit (Visit 2)	First Driving Visit (Visit 3)		Washout Period	Second Dosing Visit (Visit 4)	Second Driving Visit/ Early Exit (Visit 5)		
Visit Windows	Days -30 to -1	Day 1 (to be scheduled between 08:00 and 10:00)	Days 8 to 15		7 to 42 days	Days 15 to 57 (to be scheduled between 08:00 and 10:00)	Days 22 to 71		7- to 14-day study intervention adaptation period between Visits 2/3 and 4/5
			Before Dosing	After Dosing			Before Dosing	After Dosing	Before dosing (before study intervention instillation) and after dosing (approximately 1 hour after study intervention instillation)
Photopic conditions: perform under photopic conditions ( $\geq 80$ cd/m  ; 251 lux at target).			X	X			X	X	
Photopic, high contrast, binocular HDVA			X	X			X	X	Measurement is conducted OU only with habitual correction.
Photopic pupil diameter			X	X			X	X	Please see Section 8.1.7.
Fluorescein corneal stain	X								Please see Section 0, Item 4.02 (exclusion criteria).
IOP measurement	X	X				X			Please see Section 0, Item 4.07 (exclusion criteria).
Gonioscopy/angle assessment	X								Please see Section 0, Item 4.04 (exclusion criteria).
Dilated fundoscopic examination	X								Please see Section 8.2.1.3.
Review inclusion and exclusion criteria	X	X							Please see Section 5.1 and Section 0 (inclusion and exclusion criteria).

Procedures	Study Days (Visits)							Notes	
	Screening (Visit 1)	Randomization/ First Dosing Visit (Visit 2)	First Driving Visit (Visit 3)		Washout Period	Second Dosing Visit (Visit 4)	Second Driving Visit/ Early Exit (Visit 5)		

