#### **9.4.2. Safety Analyses**

The safety analyses will be performed using the safety population. For each safety parameter, the last nonmissing safety assessment before the first dose of study intervention will be used as the baseline.

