4.0 Analysis Populations

The following populations are defined:

Population	Description
Intent-to-Treat (ITT)	The ITT population includes all randomized participants.
Safety	The safety population includes all treated participants who receive ≥ 1 administration of study intervention.

For analyses based on the ITT population, participants will be summarized according to the randomized study intervention. For analyses based on the Safety population, participants will be summarized according to the study intervention they actually receive in each period.

Also, only statistical analyses of safety will be performed by study period as defined in Table 4-1.

Table 4-1 Definition of the Control Period

Period	Start Date	End Date
Period 1	Date of the first dose at Visit 2	
 For participants who do not receive the treatment at Visit 4: the end date is the study exit date. For participants who receive the treatment at Visit 4: the end date is the date when the treatment is received at Visit 4 minus 1 day.
Period 2	Dose date at Visit 4	Study exit date

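### SAP 9.5.3 plans an IOP change with no scheduled on-treatment reading, and Table 4-1 leaves adverse events after study exit without a treatment group (low-severity SAP correction)

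*SAP*

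**What the plan says.** **IOP.** IOP is a safety endpoint in SAP 3.3. SAP 9.5.3 says that "IOP change from baseline will be calculated for each eye" and bases the summary on whichever eye fell more. The IOP row of protocol Table 1-1 is marked at Screening, Visit 2 and Visit 4. It is blank at Visit 3 and at Visit 5/Early Exit, both before and after dosing. The row's note reads "Please see Section 0, Item 4.07 (exclusion criteria", which points to eligibility. The row stands above the instillation row, and protocol 1.3 says "Study procedures are recommended to be completed in sequence as listed in the schedule below".

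**Baseline.** In SAP 9.1, "the baseline for safety parameters will be the last assessment prior to the first administration of study intervention in the period unless specified otherwise", and "the change from baseline values will be computed as the postbaseline value minus the baseline value (defined above) for that study period". Protocol 9.4.2 differs: "the last nonmissing safety assessment before the first dose of study intervention will be used as the baseline".

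**Periods.** SAP 4.0 analyses safety by the periods of Table 4-1. For participants dosed at Visit 4, Period 1 closes early: "the end date is the date when the treatment is received at Visit 4 minus 1 day". Otherwise, "For participants who do not receive the treatment at Visit 4: the end date is the study exit date". Period 2 always ends at study exit. SAP 9.1 builds each treatment group for safety from Period 1 and Period 2 data only.

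**TEAE window.** SAP 9.2.1 and protocol 9.4.2.1 count events up to 30 days after the last dose.

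**The concern.** Two planned safety outputs do not fit the rules that feed them.

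(a) A change from baseline needs a reading after baseline. If every scheduled IOP is itself a baseline, the by-treatment IOP change table has no scheduled data. Anyone who fills it by using the protocol's single baseline would report a post-washout value, which could be taken for a drug effect.

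(b) An event can qualify as treatment-emergent and still fall in neither period. With no other attribution rule, it would drop out of the by-treatment TEAE tables although the SAP's own definition includes it.

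**Working it through.** **Schedule.** The inputs are in protocol Table 1-1: Visit 3 on Days 8 to 15, washout 7 to 42 days, adaptation 7 to 14 days. They reproduce the plan's own visit windows:

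- Visit 4 = Visit 3 + washout: 8 + 7 = Day 15 to 15 + 42 = Day 57.
- Visit 5 = Visit 4 + adaptation: 15 + 7 = Day 22 to 57 + 14 = Day 71.

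**(a) Role of each scheduled IOP reading, in the listed order**

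| Reading | Timing | SAP 9.1 with Table 4-1 | Protocol 9.4.2 |
|---|---|---|---|
| Screening | before any dose | replaced by Visit 2 | replaced by Visit 2 |
| Visit 2 | before the first dose | Period 1 baseline | baseline |
| Visit 4 | after washout, before the second-period dose | Period 2 baseline | post-baseline |
| Visits 3 and 5 | not scheduled | none | none |

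Scheduled post-baseline readings for a participant dosed at Visit 4:

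- SAP 9.1: 0 in Period 1 and 0 in Period 2. The Visit 4 reading cannot count for Period 1, which closed the day before.
- Protocol 9.4.2: 1, at Visit 4, taken 7 to 42 days after Visit 3, the last first-period dosing day.

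There is one exception. A participant who attends Visit 4 but is not dosed stays in Period 1 until exit, so that reading is post-baseline for Period 1. It is still a post-washout value.

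**(b) TEAE window against the periods**

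Completers receive their last dose at Visit 5, which is also study exit.

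- Period 2 ends on Day 22 (shortest schedule) to Day 71 (longest).
- The TEAE window ends on Day 22 + 30 = 52 to Day 71 + 30 = 101.
- Days after the last dose that lie in any period: 0 of 30.

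For a participant whose exit falls d days after the last dose, the unassigned part is max(0, 30 − d) days. Illustrations: d = 0 gives 30, d = 10 gives 20, and d = 30 or more gives 0.

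By contrast, participants dosed at Visit 4 have days after the Visit 3 dose credited to Period 1. The count is washout − 1, which is 7 − 1 = 6 to 42 − 1 = 41 days.

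**The case against.** **IOP.** The protocol does not list IOP among its safety measures, the schedule note ties it to an exclusion criterion, and protocol 9.4.2.2 leaves other safety methods to the SAP. The SAP baseline can therefore be taken as the operative one. On that reading almost nothing is computable, so little can be misread, and table programming would expose the problem. That limits the harm but does not make the planned analysis feasible. SAP Appendix D records no change from the protocol, so it does not explain the two baselines. The procedure order is only recommended, and unscheduled readings are possible, but the documents plan no on-treatment reading.

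**Choice of eye.** A reader might infer that picking the eye with the greater decrease hides IOP rises. The rule could leave out a rise in the other eye, but with almost no change score to compute the point is largely moot. Protocol 2.2 notes that pilocarpine is used to lower IOP, which may explain the rule, although the SAP gives no reason.

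**Adverse events.** The last scheduled query is at Visit 5, and protocol 8.3.1 does not oblige the investigator to seek events once participation ends. Listings of all adverse events are planned (protocol 9.4.2.1). SAP 9.2.4 summarises and lists all serious events, and SAP 9.2.2 has a row for all deaths; neither states a period limit. This stands, and it means few events are likely to be affected. It does not close the gap:

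- Protocol 8.3.1 sets collection to 30 days after the last dose.
- Protocol 8.3.3 has events followed to resolution or stabilisation.
- SAP 9.2.1 gives any worsening a new record with a new onset date. An event ongoing at Visit 5 that worsens during follow-up is then a TEAE with no period.

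**Share of events lost.** A reader might divide the 30 unassigned days by the 38- to 45-day Period 2 window (8 to 15 days plus 30) and infer that most Period 2 events are lost. The documents do not support that. These are calendar days with no scheduled query, and no event rate is given.

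**Participants not dosed at Visit 4.** It would also be wrong to take the 54 − 40 = 14 planned non-completers as the number not dosed at Visit 4, or to assume that each loses all 30 days. Protocol 7.1 encourages those who stop treatment to stay for the second driving visit, so exit may come well after the last dose.

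**Conclusion.** Both points hold on the text, at low severity.

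(a) For participants dosed at Visit 4, the IOP change in SAP 9.5.3 has 0 scheduled post-baseline readings in each period under the SAP's rules. Under the protocol's baseline it has only a post-washout value, which cannot show an on-treatment effect. This assumes that procedures follow the listed order.

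(b) A TEAE with onset after study exit has no treatment group. For completers dosed at Visit 5 this covers all 30 days after the last dose. For participants not dosed at Visit 4 it covers only what remains of the 30 days after exit. The number of events cannot be derived from the documents. It is probably small: mainly spontaneous reports and worsening found during follow-up. With 1:1 sequences, each treatment is the second one for about 54 / 2 = 27 participants, so any loss should be roughly balanced between treatments.

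The primary noninferiority test uses neither rule and is unaffected.

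**What to change.** Change the SAP wording before database lock.

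- **SAP 9.5.3:** replace the by-treatment change from baseline with observed IOP for each eye at Screening, Visit 2 and Visit 4. If Visit 4 minus Visit 2 is shown, label it post-washout, present it by sequence for each eye, and do not select one eye. State that presentation by sequence is an exception to SAP 9.1, which presents safety by intervention group.
- **SAP Table 4-1:** end each participant's last period at the later of study exit and last dose plus 30 days, assigned to the last treatment received. For participants dosed at Visit 4, leave Period 1 ending the day before that dose.

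The cost is wording only, with no added visit, procedure or data. By-treatment adverse event counts may rise slightly. Nominal follow-up still differs: Period 1 runs 14 to 56 days (Day 1 to the day before Visit 4) for participants dosed at Visit 4, and Period 2 would run 8 + 30 = 38 to 15 + 30 = 45 days for completers. Scheduled adverse event queries still end at Visit 5, so the longer window settles attribution and does not improve detection.
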